13 DATA REPORTING / REGULATORY CONSIDERATIONS

Adverse event lists, guidelines, and instructions for AE reporting can be found in Section 7.0 (Adverse Events: List and Reporting Requirements).

13.1 Data Reporting

13.1.1 Method

This study will be monitored by the Clinical Data Update System (CDUS) version 3.0. Cumulative CDUS data will be submitted quarterly to CTEP by electronic means. Reports are due January 31, April 30, July 31, and October 31. Instructions for submitting data using the CDUS can be found on the CTEP web site (<http://ctep.cancer.gov>). **Note:** All adverse events that have occurred on the study, including those reported through CTEP-AERS, must be reported via CDUS.

13.2 Cooperative Research and Development Agreement (CRADA)/Clinical Trials Agreement (CTA)

The agent(s) supplied by CTEP, DCTD, NCI used in this protocol is/are provided to the NCI under a Collaborative Agreement (CRADA, CTA, CSA) between the Pharmaceutical Company(ies) (hereinafter referred to as Collaborator(s)@) and the NCI Division of Cancer Treatment and Diagnosis. Therefore, the following obligations/guidelines, in addition to the provisions in the “Intellectual Property Option to Collaborator” (http://ctep.cancer.gov/industryCollaborations2/intellectual_property.htm) contained within the terms of award, apply to the use of the Agent(s) in this study:

1. Agent(s) may not be used for any purpose outside the scope of this protocol, nor can Agent(s) be transferred or licensed to any party not participating in the clinical study. Collaborator(s) data for Agent(s) are confidential and proprietary to Collaborator(s) and shall be maintained as such by the investigators. The protocol documents for studies utilizing investigational Agents contain confidential information and should not be shared or distributed without the permission of the NCI. If a copy of this protocol is requested by a patient or patient’s family member participating on the study, the individual should sign a confidentiality agreement. A suitable model agreement can be downloaded from: <http://ctep.cancer.gov>.
2. For a clinical protocol where there is an investigational Agent used in combination with (an)other investigational Agent(s), each the subject of different collaborative agreements, the access to and use of data by each Collaborator shall be as follows (data pertaining to such combination use shall hereinafter be referred to as "Multi-Party Data"):
 - a. NCI will provide all Collaborators with prior written notice regarding the existence and nature of any agreements governing their collaboration with NIH, the design of the proposed combination protocol, and the existence of any obligations that would tend to restrict NCI's participation in the proposed

combination protocol.

- b. Each Collaborator shall agree to permit use of the Multi-Party Data from the clinical trial by any other Collaborator solely to the extent necessary to allow said other Collaborator to develop, obtain regulatory approval or commercialize its own investigational Agent.
 - c. Any Collaborator having the right to use the Multi-Party Data from these trials must agree in writing prior to the commencement of the trials that it will use the Multi-Party Data solely for development, regulatory approval, and commercialization of its own investigational Agent.
3. Clinical Trial Data and Results and Raw Data developed under a Collaborative Agreement will be made available exclusively to Collaborator(s), the NCI, and the FDA, as appropriate and unless additional disclosure is required by law or court order. Additionally, all Clinical Data and Results and Raw Data will be collected, used, and disclosed consistent with all applicable federal statutes and regulations for the protection of human subjects including, if applicable, the *Standards for Privacy of Individually Identifiable Health Information* set forth in 45 C.F.R. Part 164.
 4. When a Collaborator wishes to initiate a data request, the request should first be sent to the NCI, who will then notify the appropriate investigators (Group Chair for Cooperative Group studies, or PI for other studies) of Collaborator's wish to contact them.
 5. Any data provided to Collaborator(s) for Phase 3 studies must be in accordance with the guidelines and policies of the responsible Data Monitoring Committee (DMC), if there is a DMC for this clinical trial.
 6. Any manuscripts reporting the results of this clinical trial must be provided to CTEP by the Group office for Cooperative Group studies or by the principal investigator for non-Cooperative Group studies for immediate delivery to Collaborator(s) for advisory review and comment prior to submission for publication. Collaborator(s) will have 30 days from the date of receipt for review. Collaborator shall have the right to request that publication be delayed for up to an additional 30 days in order to ensure that Collaborator's confidential and proprietary data, in addition to Collaborator(s)'s intellectual property rights, are protected. Copies of abstracts must be provided to CTEP for forwarding to Collaborator(s) for courtesy review as soon as possible and preferably at least three (3) days prior to submission, but in any case, prior to presentation at the meeting or publication in the proceedings. Press releases and other media presentations must also be forwarded to CTEP prior to release. Copies of any manuscript, abstract and/or press release/ media presentation should be sent to:

Email: [contact]

The Regulatory Affairs Branch will then distribute them to Collaborator(s). No publication, manuscript or other form of public disclosure shall contain any of Collaborator's confidential/ proprietary information.

14 STATISTICAL CONSIDERATIONS

14.1 Study Design/Endpoints

The primary objectives of this trial are to be a pilot study to explore the potential benefit of using imatinib mesylate in patients with cGVHD manifesting as sclerotic skin changes (ScGVHD), as well as to determine if the use of 200 mg imatinib mesylate will be tolerated by patients enrolled on the trial.

The primary endpoint for ScGVHD will be as follows: percent change in absolute ROM from baseline to 6 months.

With one primary endpoint, 10 patients will be adequate to have 80% power for a two-tailed 0.05 alpha level test to detect 1.0 SD change from baseline to 6 months for this endpoint. A paired t-test will be used to evaluate the change if the data are normally distributed. If the data are not normally distributed ($p < 0.05$ by a Shapiro-Wilks test), then a Wilcoxon signed rank test will be used instead.

In addition, as patients will be evaluated every three months, a slope parameter for the change in ROM over time will be measured. The slope (ROM vs. time) from linear regression will be computed for each patient, and with 10 patients' slopes, there will be 80% power to determine if the slopes differ from zero, using a two-sided, one sample t-test and a 1 standard deviation effect size. That is, for each patient, the slope of ROM over all of the available measurements after starting treatment will be determined, and testing will be done to see if the mean slope differs from zero; with 10 patients a mean slope greater than the standard deviation of the 10 slopes should be identifiable with a 0.05 significance level, with 80% power. In practice, if the slopes are not consistent with normality ($p < 0.05$ by a Shapiro-Wilks test), then a Wilcoxon signed rank test will be used.

Patients may drop out due to disease progression, recurrent malignancy, inability to comply with study requirements, unacceptable toxicity, or need for additional systemic therapy for cGVHD, prior to the 6-month evaluation. It is expected that this will be the case in no more than 10-20 percent of patients. In order to allow for this, up to 13 patients will be permitted to be enrolled, but accrual will stop when 10 are evaluable. Patients will only be replaced if they are not evaluable for the ROM evaluation at the 3 month time point for any reason, since this would make the slope estimate impossible to determine (in the absence of intermediate time points, which are not useful to obtain since anti-fibrotic responses are likely to be slow and thus not reflective of any benefit when possible to be identified).

There could be bias due to drop out because of progression, but this is expected to be very limited. In addition to 6-month values, the trial will also obtain intermediate values at 3 months. By having these intermediate values available, estimates from fitting a regression line or from a

'last observation carried forward' technique may be used to try to obtain reasonable substitutes for values not available from those who do not complete 6 months of observation. This type of procedure will be done with appropriate caveats if implemented.

A stopping rule based on the appearance of unresolved grade 3 or any grade 4 toxicity attributable to imatinib will be as follows: if at any time during the trial, a cumulative total of 2 patients experience this level of toxicity, no further patients will be enrolled. This is because the upper one-sided 80% confidence bound on fractions between 2 of 3 and 2 of 10 patients with toxicity extends from 0.38 to 0.93, and as such, this level of toxicity would be consistent with levels clearly considered excessive and which outweigh the potential benefit of the agent in this population.

As this is a one-arm pilot study, there is no control for natural history or regression to the mean, but improvements without the use of treatment are unlikely since this manifestation of GVHD is typically static or progressive and does not remit or improve spontaneously. Nonetheless, if results from this trial look promising, then a randomized study is indicated as the next evaluation.

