 - a. An MRI scan of one involved sclerotic skin area will be performed. The area will be determined based on severity of involvement and ability to adequately image after discussion between relevant study investigators. MRI will not be required for patients with contraindications to MRI procedure. (See section 3.5.4). Children who require sedation for MRI will be excluded.
 - b. All patients: High resolution CT scan of the chest following NIH Department of Radiology protocol for evaluation of bronchiolitis obliterans.
8. Evaluation by Ophthalmology for ocular cGVHD assessment, if indicated.
9. Evaluation by Dental Clinic for oral cGVHD assessment, if indicated.
10. Evaluation by Physiatry for ROM and functional status, includes occupational therapy (OT) assessment (Appendix S) will be performed within 2 weeks of starting therapy.
11. Evaluation by Dermatology for GVHD assessment of the skin will be performed within 2 weeks of starting therapy. A 6mm skin biopsy will be performed from an area of clinically affected skin in patients 18 years and older. This specimen will be divided for histological analysis and phospho-PDGFR studies.
12. Cardiac Evaluation: Baseline ECG and an echocardiogram or MUGA scan should be performed on all patients.
13. Quality of Life (QOL) and Functional Assessment (Appendices J-L, S): Patient-reported functional status measures include the Lee Symptom scale (Appendix K) and GVHD symptom self-assessment (Appendix L).
14. Leukapheresis (Optional): Collection of blood cells for research purpose only by a leukapheresis procedure - patient will have a consent option to decline. One pass leukapheresis will be performed in the Department of Transfusion Medicine (DTM) using standard procedure. Approximately 2-5 liters will be processed, with the goal to obtain approximately 2×10^9 cells per procedure. Leukapheresis will be offered only to subjects older than 18 years of age. The cells collected during this procedure will be used for Immune function, TGF- β , and IL-13 studies, as described in section 9.1.

11.1.2 On Study Evaluation:

1. History and physical examination, performance status at least once every other week for one month and once monthly while on treatment.
2. Laboratory Assessment (weekly for one month, every other week for 6 months and then approximately monthly thereafter): Complete blood count, differential and platelet count, electrolytes, creatinine, calcium, magnesium, phosphorus, SGPT, SGOT, bilirubin,

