12 MEASUREMENT OF EFFECT

12.1 Response Criteria

The primary endpoint for evaluation of response is established at the 6-month time point. Patients will be evaluated for response based on their ScGVHD evaluation. For the secondary endpoints, other involved organs will be evaluated, but not used in scoring for response to therapy (see appendix P).

12.1.1 ScGVHD will be measured and scored at baseline and every three months from beginning protocol treatment and will be measured by Physiatry. The ROM score will be

based on the composite joint ROM from the three most affected joints for patients with 3 or more affected joints (Appendix M, N). For those patients with fewer than 3 affected joints, the 2 most affected joints or the change in the overall ROM if only a single joint is affected. As there is not currently standardized assessment for ScGVHD, in our experience ROM assessments provide the most reproducible measure of disease progression or improvement in patients with involvement of skin and subcutaneous tissue involving joints. ROM will be measured using the American Academy of Orthopaedic Surgeons Criteria (AAOS, Chicago 1965). Percent change is based on percent change of deficit as compared to baseline. This scoring system has been successfully used in several recently published studies from the NCI evaluating the effects of anti-fibrotic agents on radiation-induced fibrosis[36,37].

As mentioned above, range of motion has been used in other clinical trials as a primary outcome measure, including trials conducted at the NIH Clinical Center studying pentoxifylline [37] and pirfenidone [36] for the treatment of radiation-induced fibrosis. There are several criteria by which ROM may be performed. Our physiatrist will perform the ROM measurements using the American Academy of Orthopaedic Surgeons Criteria (AAOS), which has been used extensively for several decades. However, reproducibility is a potential concern, and we will attempt to minimize this by the use of a single clinician who is experienced in ROM measurement. It is also important to recognize that there are no alternative validated measures of skin fibrosis in ScGVHD [32]. This emphasizes the value of the secondary objective to “establish outcome criteria for the evaluation of ScGVHD using multi-modality objective and subjective assessments, including magnetic resonance imaging, skin scoring, and patient self-reported measures”.

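### Read literally, the additional slope analysis in section 14.1 leaves out baseline ROM, although the same section's evaluability rule and regression substitute need it

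*Combined protocol and SAP*

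**What the plan says.** Section 14.1 makes the change in ROM between baseline and month 6 the primary efficacy endpoint. It then adds a slope analysis: a linear regression of ROM on time in each patient, with the slopes tested against zero. The operative definition is that "the slope of ROM over all of the available measurements after starting treatment will be determined". Its power statement is that "with 10 patients' slopes, there will be 80% power to determine if the slopes differ from zero". That figure assumes an effect of one SD of the slopes and a t-test on a single sample, two-sided at 0.05.

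The ROM schedule is in section 12.1: "ScGVHD will be measured and scored at baseline and every three months from beginning protocol treatment". Section 11.1.1, which lists the pre-treatment tests, includes as item 10 "Evaluation by Physiatry for ROM and functional status" and says it "will be performed within 2 weeks of starting therapy". Appendix B also places this examination in its pretreatment column.

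Later in 14.1, a patient is replaced only if ROM cannot be evaluated at month 3, "since this would make the slope estimate impossible to determine". Extra intermediate visits are dismissed there as not useful. For patients who do not reach month 6, the section suggests using the month-3 value, through a regression line or by carrying it forward, to supply the missing result.

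**The concern.** The slope definition admits only measurements made once treatment has begun, and baseline is made before. No sentence puts baseline into the slope, whereas the primary endpoint names it explicitly.

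The evaluability rule works differently. Because only a missing month-3 ROM triggers replacement, a patient with month 3 and nothing later counts among the 10 evaluable patients. On the literal definition that patient has one point, hence no slope and no line to extrapolate. The rule and the regression substitute make sense only if baseline is the other point.

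At stake are the number of slopes available, the precision of each, and whether the analysis sees anything that happens in the first three months. Two analysts working from this text could code different slopes and reach different results.

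**Working it through.** **Inputs.** From 14.1: 10 slopes, two-sided one-sample t-test, alpha 0.05, effect of 1 SD of the slopes, and expected dropout before month 6 of at most 10–20%. From 12.1: ROM at months 0, 3, 6 and so on. From 5.3: patients with no response at month 6 stop treatment.

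**1. The plan's power figure.** With df = 9 and noncentrality 1.0 × √10 = 3.162, the noncentral t gives 80.3%. The stated 80% reproduces.

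**2. What each definition computes up to month 6.** The least-squares weights are (t − mean t)/Sxx.
- Months 0, 3, 6: Sxx = 9 + 0 + 9 = 18; weights −1/6, 0, +1/6; slope = (ROM6 − ROM0)/6.
- Months 3, 6: Sxx = 2.25 + 2.25 = 4.5; weights −1/3, +1/3; slope = (ROM6 − ROM3)/3.

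**3. Measurement error.** Its contribution to the slope variance is σ²/Sxx. The ratio is 18/4.5 = 4, and the SDs are 0.236σ with baseline and 0.471σ without.

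**4. Number of slopes.** If 1 or 2 of the 10 evaluable patients have month 3 only, 9 or 8 slopes remain. At 1 SD, power is 74.8% or 68.1%. This is the upper end of what the dropout figure implies, because patients lost before month 3 are replaced. With baseline included, each of these patients keeps a slope, (ROM3 − ROM0)/3.

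**5. Timing of the gain.** Let G be the gain reached by month 6. With baseline the slope is G/6 whatever the path. Without it:

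| Path | Slope without baseline |
|---|---|
| all gain before month 3 | 0 |
| two thirds before month 3 | (G/3)/3 = G/9 |
| linear | (G/2)/3 = G/6 |
| all gain after month 3 | G/3 |

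If a gain of G at month 3 falls back to 0.7G at month 6, the slope is 0.7G/6 = +0.117G with baseline and −0.3G/3 = −0.10G without.

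**6. Power for a given gain, under assumptions.** The documents give no SDs. Assume a between-patient SD of gain τ of 5–10, a measurement SD s of 3–5, and a share h of every patient's gain falling after month 3. With baseline, d = G/√(τ² + 2s²); G is set so that d = 0.996, which gives 80% power. Without baseline, d′ = hG/√(h²τ² + 2s²).
- Lowest case, τ = 5, s = 5: G = 0.996 × √75 = 8.63. Linear gain (h = 0.5): d′ = 4.31/√56.25 = 0.575, power 37%.
- Highest case, τ = 10, s = 3: G = 0.996 × √118 = 10.82. Linear gain: d′ = 5.41/√43 = 0.825, power 64%.

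| Gain made by month 3 | Power without baseline |
|---|---|
| all | 5% |
| three quarters | 14–34% |
| half (linear) | 37–64% |
| one quarter | about 63–76% |
| none | 80% (no loss) |

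**The case against.** The best reply is that the authors meant baseline to be included. The slope is introduced as a change over time in patients seen every three months, the schedule starts at baseline, and the regression substitute cannot work without baseline. That is probably right. It makes this a wording defect, but it does not remove the need to correct the sentence that an analyst will program.

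A reader might infer that the stated reason for the replacement rule, "since this would make the slope estimate impossible to determine", itself proves that baseline belongs in the slope. It does not. Without baseline, losing month 3 leaves only month 6 in that period, so the slope is equally impossible. With baseline, a patient who has months 0 and 6 still has a slope. The conflict lies only in treating month 3 as sufficient and in the regression substitute.

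A reader might also infer that every early dropout loses the slope. Section 11.1.3 asks for ROM on coming off treatment, if possible and unless done in the last 4 weeks. Section 12.1.2 and Appendix B call for a repeat at 2–4 weeks when progression is suspected. Some dropouts will therefore have a second point. This narrows the gap without closing it.

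On size, 14.1 expects anti-fibrotic responses to be slow, which favours the lower rows of the last table. Responders followed to month 9 recover precision: months 3, 6 and 9 have Sxx = 18, the same as months 0, 3 and 6. Non-responders stop at month 6 and do not have those visits.

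**Conclusion.** Wrong as written, for the additional slope analysis only. The literal definition conflicts with the evaluability rule and the regression substitute in the same section, and produces a poorer slope from data that already include baseline.

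Two consequences need no outside figures: change before month 3 has no weight, and the measurement-error variance of the slope to month 6 is fourfold. The fall in power to 74.8% or 68.1% assumes that 1 or 2 of the 10 patients have month 3 only and no off-treatment or repeat ROM. The power table in step 6 rests on assumed SDs and a common shape of gain. It shows a range and does not predict this trial.

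Two stronger readings are not supported. The primary efficacy result is not compromised, because it is measured from baseline and keeps all early gain. Nor is the 80% figure in error: it is expressed in units of the slopes' own SD and holds for 10 slopes under either definition. What changes is how large that SD is, how much of the gain the slope captures, and whether 10 slopes exist.

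**What to change.** In section 14.1, replace the sentence stating that "the slope of ROM over all of the available measurements after starting treatment will be determined" with wording such as: *each patient's slope will be fitted over the pre-treatment baseline ROM (time 0) and all available on-treatment ROM measurements; a slope requires baseline and at least one on-treatment ROM.*

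The minimum should not be set at baseline plus month 3, because that would discard a patient with baseline and month 6, who has a valid slope and the primary endpoint.

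The cost is one sentence. Baseline ROM is already collected, so no visit, measurement or patient is added, and the test, the alpha and the 80% power statement stand.

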and routine infectious disease surveillance as clinically indicated. For patients with serum creatinine levels above the age-adjusted normal limits, an eGFR will be performed.

3. Urinalysis and Lymphocyte Phenotyping TBNK will be performed every 3 months.

4. Complete GVHD evaluation at the NIH will be performed every 3 months. This includes eye evaluation, dermatology assessment, oral assessment, ROM physiatry evaluation, pulmonary function tests (PFTs) if indicated, quality-of-life scales and functional assessment evaluation (including OT evaluation). NIH subspecialty exam (ie. ophthalmology, dentistry) will be employed if clinically indicated. ROM evaluation constitutes the primary study endpoint.

5. Research labs as per appendix C.

11.1.3 End of Study Evaluation:

The following tests and procedures should be performed, if possible, at the time a patient comes off treatment regardless of the reason for coming off treatment, unless the test or procedure has been performed in the last 4 weeks (2 weeks for physical examination and laboratory assessment). This evaluation should be at the NIH.

1. History and physical examination, performance status, ROM and functional assessment, and complete assessment of cGVHD including evaluation by Dermatology, Physiatry, and OT. Other evaluations such as Ophthalmology and Dental if indicated.
2. Laboratory Assessment: Complete blood count, differential and platelet count, Electrolytes, creatinine, calcium, magnesium, phosphorus, SGPT, bilirubin, and urinalysis.
3. MRI of the skin.
4. Pulmonary function tests (if indicated).
5. High resolution CT scan of the chest for patients with BO.
6. Quality-of-Life Scale.
7. Apheresis. (Optional)

At the physician's discretion, patients may be asked to return to the NIH for a one year off treatment evaluation prior to their removal from this study.

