14.1.1 Updated Statistics Amendment E

After enrolling 8 patients on the trial at the 400 mg dose initially, none of the patients were able to tolerate this dose and all required dose reduction. The five of these 8 who have been evaluable for efficacy following dose reduction will have their outcomes described when the study is reported.

Amendment E will seek to determine the tolerability of the agent at 200 mg (130 mg/m² pediatric) after initially starting at 100 mg (65 mg/m² pediatric), and to seek the same determination of level of efficacy as was intended for the original cohort. To evaluate tolerability, the study will evaluate the fraction of the first 10 patients who start at 100 mg and escalate to 200 and who are able to tolerate the drug long enough to have a 3 month efficacy evaluation. It would be desirable if a fraction consistent with 90% would be able to tolerate the agent at this dose level and not acceptable if it were consistent with 50% or lower. If among the first 10 patients enrolled, 8 or more can tolerate the drug at 200 mg, this has 93.0% probability of occurring if the true fraction tolerating the drug were 90% and only 5.5% probability of occurring if the true fraction tolerating the drug were only 50%. Thus, it would be considered acceptable tolerability if 8 or more of the first 10 enrolled in the new cohort would tolerate the 200 mg dose.

Efficacy in the 200 mg cohort would be determined using the original specifications based on the initial evaluation intended for 400 mg. Thus, up to 13 patients will be enrolled in the 200 mg cohort in order to try to obtain 10 who can be evaluated for the change in their range of motion as specified above. If appropriate based on similarity of results, the findings from the two cohorts may be combined as well as presented individually in publications resulting from the study. The study will end accrual when there are 10 who are evaluable for ROM evaluation in this cohort.

A total of 8 patients were enrolled in the first cohort. With a new requirement of up to 13 additional patients in the 200 mg cohort, the study will have an accrual ceiling of 21 patients. It

is anticipated that the maximum of 13 unique individuals who may be required to be enrolled onto this second cohort of the trial will be accrued within 2 years or sooner.

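### The replacement rule limits the range-of-motion efficacy estimate to patients who reach month 3, and the plan has no all-treated analysis beside it

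*Combined protocol and SAP*

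**What the plan says.** **Endpoint and test.** In Section 14.1 the primary efficacy endpoint is the percent change in ROM at six months, with a paired t-test or signed rank test: "10 patients will be adequate to have 80% power for a two-tailed 0.05 alpha level test to detect 1.0 SD change". A slope per patient is an additional analysis on the same 10: "the slope of ROM over all of the available measurements after starting treatment will be determined".

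**Replacement.** Section 14.1 states: "Patients will only be replaced if they are not evaluable for the ROM evaluation at the 3 month time point for any reason". The reason given is "since this would make the slope estimate impossible to determine", qualified by "in the absence of intermediate time points, which are not useful to obtain since anti-fibrotic responses are likely to be slow". Up to 13 may be enrolled, and accrual stops at 10 evaluable. Drop-out before month 6 is expected in 10–20%. The listed causes include progression, unacceptable toxicity and need for further systemic therapy.

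**Acknowledged bias.** "There could be bias due to drop out because of progression, but this is expected to be very limited". Substitutes by regression line or last observation carried forward are mentioned for patients who do not complete six months, and they rest on the month-3 value.

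**Off-treatment examination.** Section 11.1.3 asks, if possible, for an evaluation that includes ROM and Physiatry "at the time a patient comes off treatment regardless of the reason for coming off treatment", unless it was done in the previous four weeks. The Post Study column of Appendix B also marks the Physiatry ROM examination. No section says how this ROM enters the efficacy analysis.

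**Second cohort.** Section 14.1.1 applies the same efficacy specifications to the 200 mg cohort. It scores tolerability as the fraction of the first 10 who last to the month-3 evaluation. Of the first cohort it says: "The five of these 8 who have been evaluable for efficacy following dose reduction" will have their outcomes described.

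**Other sets.** Section 14.5.1 counts every treated patient for toxicity. Section 14.4 analyses secondary endpoints, including percent responding or stable, on whichever patients have data.

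**The concern.** Replacement is tied to events that treatment can cause. A patient who cannot tolerate the drug, or who needs additional systemic therapy, before month 3 is replaced by someone who gets further. The 10 ROM changes and slopes then answer the question for patients who lasted three months, not for patients given imatinib.

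Section 14.1 itself notes that there is no control arm and that promising results would lead to a randomized study. An estimate conditioned on lasting to month 3 would feed that decision with nothing beside it to show the effect of the conditioning. The bias statement covers progression only and does not mention drop-out for toxicity, which is the more direct route.

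**Working it through.** **1. The plan's own figures (all reproduce).**
- Power, one-sample (paired) t-test: n = 10, effect 1.0 SD, two-sided 0.05, noncentrality 1.0 × √10 = 3.16, 9 df. Power is 80.3% (stated 80%).
- Enrolment: 10/(1 − 0.20) = 12.5, rounded up to 13 (stated cap 13). At 10% loss, 10/0.90 = 11.1, rounded up to 12.
- Tolerability rule, 8 or more of 10: 93.0% if the true rate is 90%, and 5.5% if it is 50% (as stated).

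The arithmetic is sound. The issue is who makes up the 10.

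**2. Who can leave before month 3.** First-cycle intolerance generally ends treatment (Section 5.1). Progression after 8 weeks, unacceptable adverse events and added systemic therapy also end it (Section 5.3). More than one steroid pulse in three months counts as progression (Sections 5.2.1 and 12.1.2). These patients have no month-3 ROM, so they are replaced, and the substitutes in Section 14.1 have no month-3 value to work from.

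**3. Is a slope impossible?** A patient with a month-3 ROM and nothing later is not replaced, so baseline must count as a point. With baseline and one later ROM at T months:

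slope = (ROM at T − ROM at baseline)/T, with SE = √2·σ/T, where σ is the SD of measurement error.

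| T (months) | SE | Ratio to month 3 |
|---|---|---|
| 1 | 1.41σ | 3.0 |
| 2 | 0.71σ | 1.5 |
| 3 | 0.47σ | 1.0 |

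So an early slope is imprecise but computable whenever the Section 11.1.3 ROM exists.

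**4. How many can be left out.** At the cap, 3/13 = 23.1%. This is a ceiling: the 10–20% expectation runs to month 6, and losses after month 3 are not replaced. Section 14.2 permits 28 in all, against 21 in Section 14.1.1. If 28 governed, the second cohort could reach 28 − 8 = 20, and the ceiling would be 10/20. In the first cohort, 8 − 5 = 3 of 8 (37.5%) were not evaluable.

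**5. Illustration of size.** The documents give no ROM outcome for early stoppers. Assume that the 10 average +1.0 SD, that k stoppers average m SD, and that the SD is common. The all-treated mean is (10 + k·m)/(10 + k). Power is from 100,000 simulated trials per case.

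| k | Mean, m = 0 | Mean, m = −1 | Power, m = 0 | Power, m = −1 |
|---|---|---|---|---|
| 1 | 0.91 | 0.82 | 75% | 56% |
| 2 | 0.83 | 0.67 | 70% | 36% |
| 3 | 0.77 | 0.54 | 66% | 21% |

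Conversely, assume that the all-treated mean is zero and a share f averaging m is excluded. The evaluable mean is then −f·m/(1 − f). The chance that the 10 show a significant improvement (nominal 2.5%) is:

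| f | m = −0.5 SD | m = −1 SD |
|---|---|---|
| 10% | 3.6% | 5.0% |
| 20% | 5.4% | 10.6% |
| 3/13 | 6.3% | 13.4% |
| 37.5% | 13.4% | 39.6% |

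**The case against.** Several stronger readings are tempting, and the documents do not support them.

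- **That the 10 are patients who did not worsen.** ROM is scheduled every three months, and ROM progression needs a second examination two to four weeks later. Anyone measured at month 3 stays in, however much worse, and so does anyone who progresses later. Early worsening removes patients only through the routes in step 2.
- **That the off-treatment ROM is already in hand for everyone.** It is requested only if possible. A patient who stops in the first weeks may also fall under the four-week waiver, because the baseline examination itself can be that recent.
- **That intolerant patients vanish, or that the 28-day starting step is a hidden run-in.** The step is stated openly and those patients are enrolled and treated. All count for toxicity, and those among the first 10 count in the tolerability result, which is a primary objective.
- **That the first cohort disproves the 10–20% assumption.** Those 8 started at 400 mg, and the reasons and timing for the 3 not evaluable are not given. Three of eight is only an upper illustration.
- **That a response rate of, say, 4/10 (40%) would be reported where 4/13 (31%) is right.** Section 14.4 does not limit the denominator to the 10. It leaves the denominator open.

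Two further points have force. Section 14.1 argues that early ROM says little because response is slow, and an early value is not a six-month change. Early two-point slopes in an unweighted t-test would also add noise. These are good reasons not to alter the primary test. They do not explain leaving out patients who stopped for toxicity or worsening with no companion analysis. Exclusion of replaced patients is implied by the replacement rule and the count of 10, not stated outright, and that is itself worth clarifying.

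**Conclusion.** The point holds at moderate severity. Followed as written, the plan gives ROM change and slope conditional on reaching month 3, with selection mainly on tolerability and to a lesser degree on early worsening. The impossibility rationale is not correct for any patient with a Section 11.1.3 ROM, the substitutes do not reach replaced patients, and bias from toxicity drop-out is not mentioned.

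Up to 23% of the second cohort could be left out at the 13-patient cap. The size of the bias cannot be derived from the documents. The SD figures in step 5 rest on assumed outcomes for early stoppers and show only that the effect could be material. The stated power, cap and tolerability probabilities are correct and are not in question.

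**What to change.** Keep the replacement rule and the 10-evaluable analysis as the primary test. Then:

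1. **Section 14.1:** remove the statement that a slope cannot be determined, and name toxicity drop-out beside progression as a source of bias.
2. **Sections 14.1 and 14.1.1:** prespecify an all-treated ROM analysis, shown beside the 10-evaluable result. It should include every treated patient with a baseline and any post-baseline ROM, including the Section 11.1.3 examination.
3. **Section 14.4:** report percent responding, and percent responding or stable, with all treated second-cohort patients as denominator. Count those with no post-baseline ROM as neither responding nor stable.
4. **Reporting:** list replaced patients by reason.

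The cost is wording only, since the examination is already scheduled. The downside is a possibly less favourable estimate, with imprecise early slopes and unequal follow-up. That is why the all-treated ROM analysis should accompany the primary test and not replace it.
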